5 STUDY SUBJECTS

Disposition data, analysis population information and protocol deviations will be summarized by injection route (IM or SQ), CD388 dose, and pooled placebo and listed by injection route (IM or SQ), CD388 dose and placebo as described in [Table 3](#).

Table 3: Data Presentations for Study Subject Information

Data	Variables	Presentation
Disposition and analysis populations	Subject, completion status (i.e., completed or withdrawn from the study), reason for withdrawal from the study, analysis population determination	
Listings:
 
• Disposition,• Randomization,• Analysis populations 
Summary table including:
 
• N of subjects randomized,• N and % of subjects who completed the study,• N and % of subjects discontinued from the study by primary reason for discontinuation• N and % of subjects discontinued from the treatment by primary reason for discontinuation 
N and % of subjects included in each of the analysis populations.

Protocol deviations	Protocol deviations	
Listings:
 
• Protocol deviations,• Pharmacokinetic (PK) sample collection time deviations 
Summary table:
 
• N and % of subjects with any major deviation

5.1 Disposition

Subject disposition will be summarized for all subjects screened and randomized.

The percentages will be calculated using the number of subjects in each cohort and study drug group as the denominator.

5.2 Protocol Deviations

Deviations identified at the site will be collected in the clinic deviation tracking system (DTS) and presented in a protocol deviation listing. Protocol deviations will be listed for the safety population. The number and percentage of subjects with any major deviation will be presented.

For PK sampling time deviations, information will be derived programmatically and presented in a separate listing.

6 DEMOGRAPHIC AND OTHER BASELINE CHARACTERISTICS

Unless otherwise specified, all available data will be listed for the safety population as detailed in [Table 4](#). Summary tables for demographics and other baseline characteristics by injection route (IM or SQ), CD388 dose, and pooled placebo will be presented for safety and PK populations.

Table 4: Data Presentations for Demographic and Other Baseline Characteristics

Data	Variables	Presentation
Demographic and other baseline characteristics	Sex, age, ethnicity, race, height (cm), weight (kg) and body mass index (BMI, kg/m ²)	Listing and summary tables
Medical history	All medical history findings	Listing Note: includes coded terms (system organ class [SOC] and preferred term [PT])
Prior medications	All medications taken 30 days prior to study drug administration and concomitant medications (including vaccines, prescription medications, nonprescription medications, dietary supplements, vitamins, or herbal medications)	Listing Note: includes coded terms (anatomic therapeutic chemical [ATC] level 4 and preferred name)

Demography and baseline characteristics will be summarized using descriptive statistics.

The medical history at screening will include all queries by the medical and clinical staff related to the subject's well-being and history of relevant past medical events/experiences. Medical history will be coded to Medical Dictionary of Regulatory Activities (MedDRA) terms version 24.1 and listed by subject.

Prior medication will be coded using the World Health Organization Drug Dictionary Global B3 Sept 1, 2021, and will be listed by subject.

7 PHARMACOKINETIC ANALYSIS

The PK analysis will be carried out according to Altasciences Standard Operating Procedures (SOPs).

7.1 Missing Values

Except for predose samples (prior to the first administration), the lack of concentration values due to failure to collect the sample, a lost or compromised sample, or due to the subject's early termination from the study will be considered missing in the dataset, and no imputation will be done. Predose samples, prior to the first administration, will be imputed with zero.

If the actual collection time of a postdose PK sample is unknown, but a valid concentration value has been measured, the sample will be set to missing in the PK analysis and will be excluded from descriptive statistics but will be presented in listings.

Subjects who do not complete the sampling schedule may be included in the PK analysis for only the PK parameters that are judged not to be affected by the missing sample(s).

7.2 Measurements Below the Lower Limit of Quantitation

Concentration values below the LLOQ associated with predose and postdose collection times up to the first quantifiable sample will be assigned a value of zero, and with postdose collection times after first quantifiable sample will be replaced with missing for the non-compartmental analyses (NCA), mean PK profile representations as well as for descriptive statistic calculations. Descriptive statistics will not be determined for time points with more than 1/3rd of samples missing.

7.3 Actual Time

The NCA will be based on the actual sampling times, except for the pre-first dose predose samples, which will always be reported as zero, regardless of time deviations, provided that they were collected prior to dosing. Available time points before second dose and after first dose may be used as predose time points in some analyses.

The individual concentration/time profiles will be presented using actual sampling times whereas the mean concentration/time profiles and tables presenting summary statistics of concentration time series will be presented using nominal sampling times.

Actual times will be listed in the report.

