1.1.2. Second Single Dose, Cohorts 2A, 2B, 3A, and 3B

Table 2: Schedule of Events: Second Single Dose, Cohorts 2A, 2B, 3A, and 3B

Day (Window)	Clinical Research Unit (CRU) Inpatient Stay										Outpatient CRU Visits ^a			
	-1 (±10)	1	2	3-6	7	9	11	14	21	30	OV1 (±3)	OV2 (±5)	OV3 (±7)	OV4 ^b (±14)
Inclusion/Exclusion criteria ^c	X	X												
Complete physical with vital signs (BP, RR, HR, oral temperature, height, weight, BMI)	X													
Targeted physical with vital signs (BP, RR, HR, oral temperature)		X ^d	X	X	X			X	X	X	X	X	X	X
Safety ECG ^e	X	X			X					X				X
Laboratory evaluations (CBC with/platelets, serum chemistry, urinalysis)	X		X	X ^f	X			X	X	X	X	X	X	X
Virology screening (HBV, HCV, HIV)	X													
Virology screening (SARS-CoV-2)	X													
Urine Pregnancy ^g	X													
Drug/alcohol screen ^h	X													
Dosing of Study Drug (Cohorts 2 and 3 only)		X												
Reactogenicity/injection site inspection ⁱ		X	X	X										
PK sample collection ^j		X	X	X	X	X	X	X	X	X	X	X	X	X
Samples for metabolite identification ^k		X	X					X		X				X
Exploratory biomarker samples		predose		X ^f										
Anti-drug antibodies		predose						X		X	X	X	X	X
Nasopharyngeal swab/nasal wash collection ^l		predose	X	X	X	X	X	X	X	X				
Assess and record AEs ^m	X	X	X	X	X	X	X	X	X	X	X	X	X	X
Concomitant medications/procedures review ⁿ	X	X	X	X	X	X	X	X	X	X	X	X	X	X

Abbreviations: AEs = adverse events; BMI = body mass index; BP = blood pressure, CBC = complete blood count; COVID-19 = coronavirus disease 2019; CRU = clinical research unit; ECG = electrocardiogram; HBV = hepatitis B virus; HCV = hepatitis C virus; HIV = human immunodeficiency virus; HR = heart rate; hr = hour; ICF = informed consent form; PK = pharmacokinetic; RR = respiration rate; SARS-CoV-2 = severe acute respiratory syndrome coronavirus 2.

Schedule of Events: Second Single Dose, Cohorts 2A, 2B, 3A, and 3B

- a. For subjects in Cohorts 2A, 2B, 3A, and 3B: outpatient visits will occur at Day 45 (OV1), Day 84 (OV2), Day 126 (OV3), and Day 168 (OV4).
- b. For subjects who discontinue study early, the Day 168 procedures should be performed.
- c. Reconfirmation of inclusion and exclusion criteria (retesting of FSH not required) is to be completed at CRU check-in on Day -1 and prior to the second single dose of CD388 Injection or placebo on Day 1.

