- d. On Day 1, the targeted physical examination should be performed predose. Vital signs collection will occur predose, 6 hours postdose, and as clinically indicated.
- e. 12-lead ECG is to be performed at CRU check-in on Day -1, predose (immediately prior to study drug administration on Day 1) and 6 hours postdose (± 10 minutes), and as indicated in the Schedule. Subjects are to be resting and semi-recumbent when ECG is being conducted.
- f. Laboratory evaluations need to be performed once during the Day 3–6 interval.
- g. Urine pregnancy test is required for females of childbearing potential at CRU check-in on Day -1.
- h. Drug and alcohol screen is to be performed during the outpatient visits if vital signs are abnormal (see [Appendix 2](#)).
- i. At indicated visits, inspection of administration site and surrounding area will be performed twice daily (once between approximately 2–4 hours postdose, and once approximately 8–12 hours postdose), with any abnormal findings reported as AEs. Reactions will be rated according to the scale provided in [Table 7](#).
- j. Blood samples for PK analysis will be collected predose (-24 hour window); post-dose at 24 hours (± 30 minute window); 48 hours (± 1 hour window); 72, 96, 120, 144, 168 hours (each ± 2 hour window); and Days 9, 10, 11, 12, 14, 21, 30 (each ± 2 hour window). Postdose samples collected at outpatient CRU visits on Days 45, 60, 90, and 120 have the same windows (i.e., in \pm days) as the visits.
- k. Blood samples for metabolite identification (e.g., free zanamivir, zanamivir dimers) will be collected on Day 1 at 2 hours postdose, on Day 2 at 24 hours postdose, on Day 30, and on Day 90. Urine samples for metabolite identification will be collected on Day 1 from 0–48 hours, from 48–96 hours, and from 96–144 hours postdose, on Day 14 over a 24-hour period, and over a 24-hour period that starts on Day 29 and ends prior to CRU check-out on Day 30.
- l. Nasopharyngeal swab samples will be collected predose on Day 1, and on Days 2, 5, 7, 9, 11, 14, 21, and 30. Nasal wash collection will occur at the time of C_{max} as determined from the first single dose (approximately 144 hours after dosing).
- m. Adverse events (including influenza-like illness which will be tested for both COVID-19 and flu) will be collected for all subjects as indicated below:

Cohort	AE/SAE monitoring period from signing of Informed Consent Form:
1A, 1B	Through 4 months after the dose of study drug

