2A, 2B, 3A, 3B	Through 205 days after the last dose of study drug (Day 206 ± 10 days)

Note: the final AE assessment will be conducted via a follow-up phone call to the subject.

- n. Concomitant procedures used to treat an AE will be recorded from the time of CD388 Injection/placebo administration until the final study visit.

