Subjects in Cohorts 2A and 2B and Cohorts 3A and 3B will receive a second single dose of CD388 Injection or placebo after washout of 5 effective half-lives after the first dose if it is determined that the safety and tolerability of the first dose is acceptable upon review of the cumulative safety data. Immediately prior to the second single dose, within each dose and route, any dropouts in the sentinel groups will be randomly replaced with subjects from the main groups, retaining their original treatment assignment (i.e., subjects assigned to placebo will remain placebo, and subjects assigned to CD388 will remain CD388; this may require unblinded personnel to oversee).

The PI and Sponsor will review blinded safety data after the initial sentinel group subjects at a dose level have completed dosing and followed for the minimum observation period as determined during the first single dose. If no drug-related SAEs or drug-related Grade ≥ 3 AEs have occurred, the subjects in the corresponding main group may be dosed within 24 hours.

The dose escalation scheme is presented in [Section 1.2](#).

The Schedule of Events is presented in [Table 1](#) (first single dose, Cohorts 1A, 1B, 2A, 2B, 3A, 3B), [Table 2](#) (second single dose, Cohorts 2A, 2B, 3A, and 3B), and [Table 3](#) (single dose, Cohort 4B). All subjects will be admitted to the clinical research unit (CRU) for observation and safety assessments from Day -1 (check-in) to Day 30. Subjects will be monitored for AEs (including reactogenicity/injection site reactions and hypersensitivity reactions) and SAEs as indicated below:

Cohort	AE/SAE monitoring period from signing of ICF:
1A, 1B	Through 4 months after the dose of study drug
2A, 2B, 3A, 3B, 4B	Through 205 days after the last dose of study drug (Day 206 ±10 days)

Abbreviation: ICF = informed consent form.

Safety will also be assessed by physical examinations, ECGs, vital signs measurements, and laboratory evaluations (hematology, coagulation, serum chemistry, and urinalysis) at various time points during and after the CRU stay. Concomitant medication use will be recorded throughout the study.

Continuous 12-lead digital ECG recording will be performed using a 12-lead Holter ECG monitor as indicated below:

Cohort	Holter Monitoring Period
1A, 1B	1 hour before administration of study drug until 48 hours after dosing
2A, 2B, 3B	1 hour before first administration of study drug until 48 hours after dosing ^a

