3 STUDY DESIGN

3.1 General Description

This is a first-in-human (FIH), Phase 1, single-center, prospective, randomized, double-blind study of ascending single doses of CD388 Injection administered IM or SQ to healthy adult subjects followed by another single dose of CD388 Injection administered by the same route 3 months or 5 effective half-lives, whichever is longer, after the first dose in the middle and high dose groups (dosing may be adjusted for tolerability). The goals are to assess safety, tolerability, immunogenicity (anti-drug antibodies [ADA]), and PK of CD388.

Dose levels of CD388 to be assessed will follow an ascending single dose design with the starting dose based on findings from 3-month rat and monkey toxicology studies. Within each route (IM and SQ dose, route assignment is unblinded), subjects will be randomized to receive a single dose of CD388 Injection or saline placebo (treatment assignment is blinded) according to the design. It should be noted that each cohort will be divided into 2 groups identified as “sentinel” groups (randomized 1:1) and “main” groups (randomized 7:2):

- Low dose level: Cohort 1A (IM) and Cohort 1B (SQ) – each route n = 2 sentinel and n = 9 main
- Mid dose level: Cohort 2A (IM) and Cohort 2B (SQ) – each route n = 2 sentinel and n = 9 main
- High dose level: Cohort 3A (IM) and Cohort 3B (SQ) – each route n = 2 sentinel and n = 9 main
- Highest dose level: Cohort 4B (SQ) – n = 2 sentinel and n = 9 main

For each route, the sentinel or first group of 2 subjects (1 CD388: 1 placebo) at a dose level will be administered blinded study drug and closely monitored for safety for at least 1 week. If no drug-related SAEs or drug-related Grade ≥ 3 AEs have occurred, the subjects in the corresponding main group may be dosed within 24 hours. The observation duration may be adjusted for the sentinel groups in Cohorts 2A, 2B, 3A, 3B, and 4B based on data from previous cohorts.

Subjects in Cohort 4B will receive a single dose of CD388 or placebo. Subjects in Cohorts 2A and 2B and Cohorts 3A and 3B will receive a second single dose of CD388 Injection or placebo after washout of 3 months or 5 effective half-lives, whichever is longer, after the first dose if it is determined that the safety and tolerability of the first dose is acceptable upon review of the cumulative safety data.

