7.4 Non-Compartmental Analysis

The following configuration for the NCA of CD388 in plasma or nasopharyngeal concentrations (with Phoenix® WinNonlin® version 8 or higher) will be used:

- Data: Serial sampled data
- Model/Dose options Type: Plasma (200 -202) / Extravascular
- AUC Calculation Method: Linear Up/Log Down
- Lambda Z (λ_z) calculation: Best fit method for λ_z Linear-Log regression

Reasons for excluding PK parameters will include the following:

- AUC: AUC parameters will not be estimated if less than 3 consecutive measurable concentrations are observed.

PK parameters requiring λ_z estimation (e.g., and $t_{1/2}$) will be set to Not Reported (NR) in the Tables and Listings if they meet the following:

- $R^2 < 0.8$

The PK parameters for CD388 are presented in [Table 5](#).

Table 5: Pharmacokinetic Parameters of CD388 in Plasma

PK Parameter	Definition
Plasma Concentrations	
C_{max}	Maximum observed concentration
t_{max}	Time of maximum observed concentration; if it occurs at more than one time point, T_{max} is defined as the first time point with this value
AUC_{0-t}	Area under the concentration time curve from time 0 (dose administration) to the time of last quantifiable concentration (t_{last})
$AUC_{0-\infty}$	Area under the concentration time curve extrapolated to infinity, calculated as $AUC_{0-t} + C_{LQC}/\lambda_z$, where C_{LQC} is the measured concentration at time t_{last} and λ_z is the apparent elimination rate constant, estimated by linear regression of the terminal linear portion of the log concentration versus time curve
$t_{1/2}$	Terminal elimination half-life, calculated as $\ln(2)/\lambda_z$
CL/F	Apparent total clearance, calculated as Dose/ $AUC_{0-\infty}$
V_z/F	Apparent volume of distribution, calculated as Dose/ $\lambda_z * AUC_{0-\infty}$
Nasopharyngeal Concentrations	
C_{max}	Maximum observed concentration
t_{max}	Time of maximum observed concentration
AUC_{0-t}	Area under the concentration time curve from time 0 (dose administration) to the time of last quantifiable concentration (t_{last})
Plasma Concentrations	
The following plasma PK parameters will be used for PK calculation and presented in the listings only	
$AUC_{\%ext}$	Extrapolated area (i.e. percentage of $AUC_{0-\infty}$ due to extrapolation from t_{last} to infinity)
R^2	Goodness of fit statistic for the terminal elimination phase
Number of Points	Number of data points in computing λ_z

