			N Mean SD Min Median Max CV% GeoMean GeoMean CV%					
NC: Not Calculated								

x = 1 through 8 for Cohorts 1A, 1B, 2A, 2B, 3A, 3B, and 4B and PK Completer Population (Cohorts 2A, 2B, 3A and 3B only)
 <DOSE> = 50 mg, 150 mg, 450 mg and 900 mg for Cohorts 1A/1B, 2A/2B, 3A/3B, and 4B, respectively.
 <ADMIN> = Intramuscular Injection for Cohorts 1A, 2A, and 3A or Subcutaneous Injection for Cohorts 1B, 2B, 3B, and 4B.
 <COHORT> = Cohorts 1A, 1B, 2A, 2B, 3A, 3B, and 4B.

Programming Note:

Table 14.2.1.2.2.x: "Descriptive Statistics of Plasma CD388 Pharmacokinetic Parameter Estimates Following a Repeated Single <ADMIN> of <DOSE> CD388 to Healthy Subjects (<COHORT>)" will follow the same layout.

Table 14.2.2.2.1.x: "Descriptive Statistics of Nasopharyngeal CD388 Pharmacokinetic Parameter Estimates Following a Single <ADMIN> of <DOSE> CD388 to Healthy Subjects (<COHORT>)" will follow the same layout.

Table 14.2.2.2.2.x: "Descriptive Statistics of Nasopharyngeal CD388 Pharmacokinetic Parameter Estimates Following a Repeated Single <ADMIN> of <DOSE> CD388 to Healthy Subjects (<COHORT>)" will follow the same layout.

Table 14.2.8 Template T2.3: PK Parameters Assessment of CD388 for <Cohort> SQ relative to IM – (Pharmacokinetic Population)

Table 14.2.3.1
 Statistical Analysis of Plasma CD388 Pharmacokinetic Parameters Between IM and SQ Administration
 (PK Population)

Dose	Parameter (unit)	n	Geometric LSmeans [1]		SQ/IM Ratio (%)	90% Confidence Interval (%)	
			IM Route	SQ route		Lower Bound	Upper Bound
xx mg	C_{\max} (unit)	xxx	xxxxxx	xxxxxx	xxx	xxx	xxx
	AUC_{0-t} (unit)	xxx	xxxxxx	xxxxxx	xxx	xxx	xxx
	$AUC_{0-\infty}$ (Unit)	xxx	xxxxxx	xxxxxx	xxx	xxx	xxx
...							
Date: VERSION – YYYY-MM-DD			Data Source: XXXX			Program Source: XXXXX.sas	

IM = Intramuscular(Reference); SQ = Subcutaneous(Test)

[1] Geometric Least Square (LS)means are based on the exponential of LSmeans of ln-transformed values
 Note(s):

An analysis of variance (ANOVA) was performed on the ln-transformed parameters with the following fixed factors: Injection route.

The ratio and 90% confidence interval (CI) were obtained by exponentiating the resulting difference between each comparison of interest (IM to SQ) least-squares means and its corresponding 90% CI.

Table 14.2.10 **Template T2.4: Dose Proportionality Analysis – (Pharmacokinetic Population)**

Table 14.2.4.1
 Dose Proportionality Analysis of Plasma CD388 Pharmacokinetic Parameters
 (PK Population)

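### Second-dose AUC and CL/F have no correction for residual first-dose drug: a one-directional bias of about 3% at 5 half-lives

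*SAP*

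**What the plan says.** SAP 3.1 gives the second dose "after washout of 3 months or 5 effective half-lives, whichever is longer, after the first dose". Protocol 6.1 opens with the same rule, but its later paragraph on Cohorts 2 and 3 drops the 3-month limb: "after washout of 5 effective half-lives after the first dose if it is determined". The two statements need reconciling.

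SAP 7.4 sets one extravascular NCA configuration, and its Table 5 has one definition per parameter. Cmax is the observed maximum. AUC0-∞ is AUC0-t plus the last quantifiable concentration over λz. CL/F is "Apparent total clearance, calculated as Dose" over AUC0-∞, and Vz/F uses the same AUC0-∞. None of these has a term for drug present at time 0. The programming note to shell Template T2.2 applies the same layout to the second dose: "Descriptive Statistics of Plasma CD388 Pharmacokinetic Parameter Estimates Following a Repeated Single <ADMIN> of <DOSE> CD388 to Healthy Subjects".

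On the pre-dose value itself:
- SAP 7.1 and 7.3 force only the sample before the first dose to zero.
- SAP 7.2 sets a pre-dose value to zero if it is below the LLOQ.
- Protocol Table 2, footnote j, schedules a PK sample before the second dose.
- SAP 7.3 adds: "Available time points before second dose and after first dose may be used as predose time points in some analyses". It does not say which analyses, or how the points are used.

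**The concern.** Dividing one dose by an AUC that also contains the tail of an earlier dose gives a clearance that is too low. The second-dose profile is the sum of two curves, and the formula credits all of it to the second dose. The error always has the same sign: AUC up, CL/F and Vz/F down. It grows with the subject's half-life.

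Repeat-dose plasma PK is a secondary objective, with up to 32 CD388 subjects (8 in each of four cohorts). SAP 4 defines a PK Completer Population of subjects who received both doses, and shells T2.1 and T2.2 list tables for it. Anyone reading first- and second-dose tables together would see slightly higher exposure and slightly lower clearance after re-dosing even if nothing had changed. The sample that would allow a correction is already drawn, but the plan has no rule for using it.

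**Working it through.** The documents state no residual fraction or carry-over size, so there is no figure of the plan's own to reproduce.

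**Inputs**
- Washout: 5 effective half-lives (SAP 3.1; Protocol 6.1).
- Reference half-life: not stated. Protocol Table 1, footnote a, places first-dose visits OV2 to OV4 in Cohorts 2 and 3 at about 2, 3 and 4 half-lives. Table 2, footnote a, places the second-dose visits at Days 84, 126 and 168. If the spacing is the same, 84/2 = 126/3 = 168/4 = 42 days, and 5 half-lives is 210 days, longer than 3 months. This is an inference. The 205-day follow-up gives 205/5 = 41 days if it was also meant as 5 half-lives.
- Tmax: about 144 hours, or 6 days (Protocol Table 2, footnote l).
- Between-subject CV of half-life: not given, so a range is shown.

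**Step 1, residual amount.** Residual = 0.5^(washout/half-life) = 0.5^5 = 3.125%. This needs no value for the half-life. At 42 days, the ±10-day check-in window moves it to 0.5^(200/42) = 3.7% or 0.5^(220/42) = 2.65%.

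**Step 2, effect on the parameters.** Take a one-compartment model with first-order absorption and superposition. The 42-day half-life gives k = ln 2/42 = 0.0165 per day, and Tmax of 6 days gives ka = 0.621 per day.
- Relative excess in AUC0-∞ = [ka/(ka − k)] × 0.5^5 = 1.027 × 0.03125 = 3.2%. AUC from 0 to 168 days is also 3.2% high.
- CL/F: 1/1.032 − 1 = −3.1%. Vz/F shifts by the same proportion, because both curves decline with the same λz.
- Observed Cmax is about 3.2% above what dose 2 alone would give.

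**Step 3, slower eliminators.** A 9% residual needs a half-life of 5/log2(1/0.09) = 1.44 times the reference. Such a subject has AUC about 9.2% high and CL/F about 8.4% low. With lognormal half-life and the reference as median, P(residual ≥ 9%) = 1 − Φ(ln 1.44/σ), where σ = √ln(1 + CV²):

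| Assumed CV | Mean residual | Share at ≥ 9% | Expected of 32 |
|---|---|---|---|
| 10% | 3.3% | 0.01% | 0.0 |
| 20% | 3.6% | 3.3% | 1.1 |
| 30% | 4.2% | 10.7% | 3.4 |
| 40% | 4.9% | 17.2% | 5.5 |

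**Step 4, does the correction work?** By time 210 days absorption of dose 1 is over, so its remaining curve is C_predose × exp(−λz t), with area C_predose/λz to infinity. Subtracting that from the second-dose AUC0-∞ returns the single-dose area exactly under linear PK. Up to the last quantifiable time, the term is (C_predose/λz) × (1 − exp(−λz t_last)).

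**The case against.** The strongest reply is that the design already limits carry-over. Five half-lives leave about 3%, the protocol calls for descriptive summaries without hypothesis testing, and SAP 7.5.2 specifies no dose-2 versus dose-1 contrast. With a PK parameter CV of 20% to 30% (assumed), the standard error of an 8-subject mean is 20%/√8 = 7% to 30%/√8 = 11%, at least twice the bias. All of this stands, and it keeps the point modest. It does not remove it: imprecision is visible in the reported CV%, while a bias in the formula is not.

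The correction also assumes linear, unchanged elimination, and it cannot be applied where λz is not reportable (R² < 0.8 in SAP 7.4). This stands too, and is why uncorrected values should stay beside the corrected ones. The optional population PK analysis in Protocol 12.4 could model both doses jointly, but it is reported separately and does not repair these tables.

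Four stronger readings are tempting but not supported:
- A reader might infer that the plan treats pre-dose-2 drug as absent. It does not. Only the pre-first-dose sample is forced to zero, and between-dose points may be used. The fault is an undefined option together with formulas that lack a residual term.
- A reader might take 9% or more as an expected result for slow eliminators. It depends on a half-life variability that the documents do not give.
- A reader might infer that carry-over would hide exposure loss due to anti-drug antibodies. That is speculative. No between-dose contrast is specified, the individual ratios in SAP 7.5.2 name no periods, and faster clearance would itself shrink the residual.
- Protocol 6.5 describes about 120 days for the first-dose period. A second dose then would leave 0.5^(120/42) = 14%, but the washout rule does not permit that timing at a 42-day half-life.

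**Conclusion.** The point holds in a limited form. Followed as written, SAP 7.4 yields second-dose AUC about 3% too high, and CL/F and Vz/F about 3% too low, for a subject with the reference half-life. The direction is certain under superposition. The 3.1% residual rests only on a washout of exactly 5 half-lives. It would be smaller if the 3-month limb governed, and larger if the terminal half-life exceeds the effective one. The 42-day half-life, the 210-day interval and every statement about spread between subjects are inferences or assumptions.

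Cmax is not in error. As the observed maximum it is the exposure the subject had, and it is the right figure to read beside second-dose safety data. The change is worth making because it affects a secondary endpoint and costs little; it does not threaten the study's conclusions.

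**What to change.** Add a paragraph to SAP 7.4 for the second-dose period only:
- Compute AUC0-∞ minus C_predose/λz, and AUC0-t minus (C_predose/λz)(1 − exp(−λz t_last)), from the subject's own measured pre-second-dose concentration and own λz. State which period's λz is used.
- Derive CL/F and Vz/F from the corrected AUC0-∞.
- Report corrected values beside uncorrected ones in Tables 14.2.1.2.2.x.
- Keep Cmax as the observed maximum.
- Flag subjects whose pre-dose level exceeds 5% of second-dose Cmax. The reference subject sits near 3.5%.
- Leave subjects without a reportable λz uncorrected, and flag them.

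Replace the open sentence in SAP 7.3 with one that names the analyses using between-dose points.

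The cost is one paragraph and a short programming step. The pre-dose sample is already scheduled and λz is already estimated. The downside is the reliance on linear, unchanged elimination, and a table in which a few subjects may have no corrected value. Showing both versions means no information is lost.
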